8.2 Data processing

Data pooling:

If a second recruitment round occurs in 2018 (see section 5.2, page 13), the data collected during the two rounds will be pooled before the main analysis. The year of integration in the study will be considered the baseline year (i.e. 2017 for the NHs of the first round, 2018 for the second round). The main analysis will then take place after data follow-up collection for the second round (planned in January 2020).

Primary outcome:

As described in section 7.2 (page 16), drug consumption data will be processed using a list of inappropriate drugs, to elicit each line's appropriateness status (probably inappropriate, possible inappropriate, not inappropriate). For each data line, the number of galenic units will be determined by lookup in a database, created by the CPC, containing information about therapeutic products used in Switzerland. The overall proportion of galenic units considered inappropriate (possibly and probably inappropriate) will then be computed for each NH using the following formula:

(total number of inappropriate galenic units used during the period)
(total number of galenic units used during the period)

The difference between baseline and 12 months will then be computed for each NH.

Co-primary outcome:

Using the same dataset as for the primary outcome and the same appropriateness classification tool, the overall number of potentially inappropriate DDD/res (possibly and probably inappropriate) will be computed using the following formula:

 $\frac{(number\ of\ boxes\ used)\cdot (number\ of\ galenic\ units\ per\ box)\cdot (dose\ per\ galenic\ unit)}{(DDD\ according\ to\ ATC\ code\ and\ administration\ route)\cdot (days\ spent\ in\ the\ NH\ during\ the\ year)}$

Secondary outcomes:

Difference in proportion of probably inappropriate galenic units and of possibly inappropriate galenic units: the difference in the proportion of possibly inappropriate drugs and of probably inappropriate drugs will be computed for each NH using the same method as for the primary outcome.

Difference in proportion of probably inappropriate DDDs and of possibly inappropriate DDDs: for each data line, the number of DDDs will be computed by multiplying the number of galenic units with the number of DDD per galenic unit. The latter is present in the database used created by the CPC for the monitoring of the cantonal PAPs. The change in proportion of possible inappropriate DDDs and probably inappropriate DDDs will then be computed as for the primary outcome.

Difference in number of possibly and probably inappropriate DDD/res: the change between baseline and 12 months will be computed for each category as for the co-primary outcome.

Number of hospital days per mean resident and per year: for each year, NH will report the total number of days spent in the hospital (i.e. days spent outside of the NH for medical reasons). The total number of days spent in the NH will be provided by the CPC monitoring team; the mean number of days in hospital per year and per mean resident will then be computed using the following formula:

 $(total\ number\ of\ days\ in\ hospital)/(total\ number\ of\ days\ spent\ in\ NH)/365$

If other data regarding hospitalisations are analysed (see section 7.3), they will be processed as described here for the total number of falls.

Mortality rate: NH will report the number of residents having died during each year. The annual mortality rate will then be computed for each NH using the following formula:

 $(total\ number\ of\ deaths)/(total\ number\ of\ days\ spent\ in\ NH)/365$

Number of falls per mean resident and per month: for each year, NH will report the number of falls. The monthly number of falls per mean resident will then be computed for each NH using the following formula:

 $(total\ number\ of\ falls)/(total\ number\ of\ days\ spent\ in\ NH)/365$

If other data regarding falls are analysed (see section 7.3), they will be processed as described here for the total number of falls.

Number of restraints measures per mean resident and per month: for each year, NH will report the number of restraint measures episodes enacted. The number of falls per mean resident and per year will then be computed for each NH using the following formula:

(total number of restraint measures episodes)/(total number of days spent in NH)/365

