4.2 Primary and secondary endpoint/outcome(s)

1) Effectiveness study:

The primary outcome is the difference in the proportion of galenic units considered as potentially inappropriate, relative to the total number of galenic units used in the NH, between baseline and 12 months. Each drug used in the NH will be assessed for appropriateness using a custom screening tool combining criterion from the Beers' list [6], the STOPP tool [31] and the NORGEP-NH list [32].

The co-primary outcome is the change in the number of potentially inappropriate defined daily dose per average resident and per day (DDD/res), between the first and second year of the study. The defined daily dose (DDD) for each drug will be computed according to its active ingredient and route of administration.

Secondary outcomes include the difference in PIMs use taking into account the DDD for each drug used in the participating NHs the number of DDD/res categorised either possibly or probably inappropriate, the annual mortality rate, the number of hospitalisation days per mean resident and per year, the number of falls per mean resident and per year, and the number of times restraint measures are used per mean resident and per year.

2) Implementation study:

The main implementation outcomes will be the adoption of the deprescribing-specific interdisciplinary quality circle module and the fidelity to it, as well as the adoption of deprescribing consensus; other implementation outcomes as costs of the intervention, satisfaction of the healthcare professionals will also be evaluated. A list of all implementation outcomes is available in Annex 1.

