### Secondary outcomes

Difference in proportion of probably inappropriate galenic units and of possibly inappropriate galenic units: the baseline to 12-month difference in the proportion of possibly inappropriate drugs and of probably inappropriate drugs will be computed for each NH using the same method as for the primary outcome.

Difference in proportion of probably inappropriate DDDs and of possibly inappropriate DDDs: for each data line, the number of DDDs will be computed by multiplying the number of galenic units with the number of DDD per galenic unit. The latter is present in the database used created by the CPC for the monitoring of the cantonal PAPs. The change in proportion of possible inappropriate DDDs and probably inappropriate DDDs will then be computed as for the primary outcome.

Number of hospital days per mean resident and per year: for each year, NH will report the total number of days spent in the hospital (i.e. days spent outside of the NH for medical reasons). The total number of days spent in the NH will be provided by the CPC monitoring team; the mean number of days in hospital per year and per mean resident will then be computed using the following formula:

$$(total\ number\ of\ days\ in\ hospital)/(total\ number\ of\ days\ spent\ in\ NH)/365$$

Mortality rate: NH will report the number of residents having died during each year. The annual mortality rate will then be computed for each NH using the following formula:

$$(total\ number\ of\ deaths)/(total\ number\ of\ days\ spent\ in\ NH)/365$$

Number of falls per mean resident and per month: for each year, NH will report the number of falls. The monthly number of falls per mean resident will then be computed for each NH using the following formula:

$$(total\ number\ of\ falls)/(total\ number\ of\ days\ spent\ in\ NH)/365$$

Number of restraints measures per mean resident and per month: for each year, NH will report the number of restraint measures episodes enacted. The number of falls per mean resident and per year will then be computed for each NH using the following formula:

$$(total\ number\ of\ restraint\ measures\ episodes)/(total\ number\ of\ days\ spent\ in\ NH)/365$$

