## Inferential analysis

The analysis will follow the intention to treat approach. However, it is expected that all NH comply with the intervention group they have been randomized into.

No formal statistical tests will be applied to compare NH groups for the variables measured before randomization.

If the primary outcome follows a normal distribution and variances between intervention groups are equal, NH groups will be compared by means of linear least-square regression under adjustment for baseline. In case of heteroscedasticity, a robust estimation of the variance will be applied. If the outcome does not follow a sufficiently normal distribution, a generalised linear model (GLM) will be applied with the most appropriate distribution and link function. Residual diagnostics will be used to check the quality of the statistical model. If it is not possible to find an acceptable model, the two NH groups will be compared by means of a Mann-Whitney test without baseline adjustment.

The same procedure will be used to compare the differences between baseline and 12 months for the proportion of probably inappropriate galenic units and of possibly inappropriate galenic units (two variables), the proportion of probably inappropriate DDDs and of possibly inappropriate DDDs (two variables) and for mortality rate.

The number of hospital days/mean resident/year, number of falls/mean resident/month; and number of restraint measures/mean resident/month, being counts, are likely to follow a Poisson distribution. Therefore, a GLM with family Poisson and logarithmic link function will be applied first.

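### The four secondary rate formulas lack brackets around resident-years, and falls and restraints carry a per-month label that the formula, even as probably intended, does not produce

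*Protocol*

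**What the plan says.** Protocol 8.2 and the SAP's Secondary outcomes section give the same unbracketed expression for all four outcomes. The numerator is the year's total of hospital days, deaths, falls or restraint episodes. The rest is as in the restraint formula: "total number of restraint measures episodes)/(total number of days spent in NH)/365".

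The stated period differs by outcome and by place:

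- **Hospital days:** per mean resident and per year in both documents.
- **Mortality:** annual. The SAP introduces the formula with "The annual mortality rate will then be computed for each NH using the following formula", and protocol 8.2 does the same.
- **Falls:** headed per month in protocol 8.2 and the SAP, and the text agrees: "The monthly number of falls per mean resident will then be computed for each NH using the following formula". Protocol 4.2 instead lists "the number of falls per mean resident and per year", and the synopsis and 7.3 also say per year.
- **Restraints:** headed per month in protocol 8.2 and the SAP. The sentence introducing the formula says per year and names falls instead of restraint measures. The synopsis, 4.2 and 7.3 say per year.

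The SAP's Descriptive analysis and Inferential analysis carry the monthly unit forward, the latter as "number of falls/mean resident/month; and number of restraint measures/mean resident/month". Protocol 5.3 states that all data are collected yearly. None of the formulas contains a factor of 12.

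**The concern.** There are two separate faults. First, the printed expression is not a rate per mean resident per year unless brackets are supplied. Second, once they are supplied, a formula that gives an annual value is attached to a monthly label for falls and, in most places in 8.2 and the SAP, for restraints.

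Protocol 7.3 describes these four as both efficacy and safety outcomes. If the faults remain, group means, adjusted absolute differences and their confidence limits would be on the wrong scale or under the wrong unit. Anyone comparing the reported falls or restraint rates with other data could be misled.

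**Working it through.** **Inputs.** Let E be the year's count (protocol 5.3: yearly totals) and D the total days spent in the NH that year. The documents give no numerical value for any of these rates, so there is no stated figure to reproduce. The check is one of units.

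**Step 1: the target.** Mean residents over the year = D/365. Therefore:

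- rate per mean resident per year = E/(D/365) = 365 × E/D
- rate per mean resident per month = 365 × E/(12 × D)

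**Step 2: the expression as printed.** E/D/365, evaluated left to right, equals E/(365 × D).

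- Annual target ÷ printed value = (365 × E/D) ÷ (E/(365 × D)) = 365² = 133,225
- Monthly target ÷ printed value = 133,225/12 ≈ 11,102

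**Step 3: the bracketed reading.** E/(D/365) is the annual rate exactly. Against a monthly label it is too high by a factor of 12.

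**Step 4: illustration.** Assumed NH, not from the documents: 50 residents, so D = 50 × 365 = 18,250, with the counts shown.

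| Outcome (assumed count) | As printed, E/D/365 | E/(D/365), per year | Per month |
|---|---|---|---|
| Hospital days (200) | 0.0000300 | 4.0 | not used |
| Deaths (12) | 0.0000018 | 0.24 | not used |
| Falls (100) | 0.0000150 | 2.0 | 0.167 |
| Restraint episodes (60) | 0.0000090 | 1.2 | 0.10 |

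On the bracketed reading the first two rows match their labels. The falls row would show 2.0 under a monthly label when the monthly value is 0.167. The restraint row would show 1.2 when the monthly value is 0.10.

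**Step 5: effect on comparisons.** The factor is the same constant for every NH. A ratio of group means does not change. In a linear regression on group and baseline, the group coefficient and its standard error are multiplied by the same constant, so the p-value does not change. Absolute differences and their limits do change, by the full factor. The primary and co-primary formulas in protocol 8.2 contain no division by 365.

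**The case against.** The best defence is that these are formulas in prose, not code. The outcomes are named per mean resident, and mean residents are days/365, so the missing brackets are obvious. No analyst would let an annual mortality of 0.0000018 stand. With the brackets supplied, hospital days and mortality are right, and the sentence introducing the restraint formula itself says per year. Three of the four formulas then match the period in their own introducing sentence. The outcomes are secondary, and protocol 7.3 makes analysis of certain falls, hospital-stay and restraint data conditional on a majority of NHs being able to supply them.

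Most of this stands. A reader might infer from the printed text that all four rates will be reported wrongly. That holds only if the formulas are typed verbatim, and the wording of the outcomes points to the bracketed form.

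It does not dispose of the monthly label. Falls are monthly in both heading and text of 8.2 and the SAP. Restraints are monthly in the heading of both, and both outcomes are monthly in the SAP's descriptive and inferential sections. A 12-fold mislabel is also far less conspicuous than a factor of 133,225.

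A reader might further infer that the choice of unit decides statistical significance, because the SAP first applies a Poisson model with log link to hospital days, falls and restraints. If the rate itself were the response, with model-based standard errors and no offset, moving from per year to per month would multiply the standard error of the log rate ratio by √12 = 3.46. The SAP gives only the family and link for that model and is silent on offset and variance. That is a separate gap in the model specification, and the formulas and labels do not establish such an effect.

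**Conclusion.** The point holds in this form. As literally written, all four formulas fail to give a rate per mean resident per year and are too small by 133,225. On the likely intended reading, hospital days and mortality are correct. What remains is a 12-fold mislabel for falls, and for restraints wherever they are headed or analysed per month, together with a contradiction of the per-year definitions in the protocol synopsis, 4.2 and 7.3.

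The consequence is limited to the scale of reported rates and absolute differences for secondary efficacy and safety outcomes. Group ratios, linear-model p-values and the primary and co-primary outcomes are untouched. It should be fixed before analysis, but it does not put the trial's main conclusion at risk.

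The factors 133,225 and 12 follow from the formulas alone. Only the illustrative rates rest on the assumed 50 residents and event counts.

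**What to change.** In protocol 8.2 and the SAP's Secondary outcomes:

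1. Write all four formulas as count/[(days spent in NH)/365].
2. Label falls and restraints per mean resident and per year, as in the protocol synopsis, 4.2 and 7.3, and carry this into the SAP's Descriptive analysis and Inferential analysis. If a monthly figure is kept, divide by a further 12 and say so everywhere, including the outcome definitions.
3. In the sentence introducing the restraint formula, replace the number of falls by the number of restraint measures.

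The cost is a wording change to four formulas in each document, the falls and restraint labels, and one sentence. No new data are needed.

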8.3 Planned analysis

Descriptive statistics

Participating NH will be described, by group, in terms of number of beds, mean age of residents, mission (geriatric, psycho-geriatric or mixed), and number of nurses, physicians and pharmacists. Each implementation outcome (list available in Annex 1) will be presented with a suited summative data.

Inferential statistics

The main outcome is the difference in the overall proportion of PIMs used in the NH 12 months after intervention, relative to baseline. The primary analysis will test the difference in the overall proportion of PIMs between the intervention and control groups using a generalised linear regression model, taking the difference in overall proportion of PIMs at 12 months as the dependant variable, and the group allocation (binary variable) and baseline overall proportion of PIMs as independent variables (two-sided α = 0.05). The analysis will be made immediately after the completion of follow-up data collection.

The same analysis will be carried out for the co-primary outcome, with the overall number of potentially inappropriate DDD at 12 months as dependent variable, adjusted for baseline value, taking into account the group allocation.

Generalised linear models will also be used to assess differences in secondary outcomes between the two groups will be tested with the same method as the primary outcome, taking the baseline value and the group allocation as the independent variables, with two-sided $\alpha = 0.05$. If enough supplementary data on falls and hospitalisations are available (see section 7.3 page 19), they will be analysed as the number of falls, respectively the number of hospital days, per mean resident and per year.

All analyses will be made using the Stata statistical package (StataCorp LP, College Station, TX, USA).

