Project design:	Effectiveness-implementation hybrid design: 1) Cluster randomised controlled trial of a nursing-home level intervention; 2) Mixed method approach to evaluate implementation strategies.									
Background and Rationale:	Older people residing in nursing homes (NH) are frequently polymedicated and often prescribed potentially inappropriate medications. Deprescribing has been proposed as a way to reduce the number of drugs they receive and their exposure to harmful treatments. In the nursing homes of Vaud and Fribourg, physicians, nurses and pharmacists are already working together in quality circles to improve drugs use. This provides an excellent opportunity to implement a deprescribing intervention, using the collaboration already in place.									
Objectives:	 To evaluate the effect of a deprescribing-specific interdisciplinary quality circle module on the use of potentially inappropriate medication in nursing-home residents. To determine the effective strategies to reach and implement deprescribing consensus resulting of said quality circle module. 									
Endpoints:	 a. The primary outcome is the change at 12 months, relative to baseline, in the proportion of PIMs used in the NHs relative to their total drug consumption; b. The co-primary outcome is the change at 12 months, relative to baseline, in the number of potentially inappropriate defined daily dose per average resident and per day (DDD/res); c. The secondary outcomes are the change at 12 months in the proportions of defined daily doses (DDD) of PIMs used in the NHs in the number of DDD/res considered to avoid or to reevaluate; the number of days in hospital per resident and per year, the number of falls per resident and per year; the number of uses of restraint measures per resident and per year, and the mortality rate. The implementation outcomes are the adoption of the deprescribing-specific interdisciplinary quality circle module and the fidelity to it, as well as the adoption of deprescribing consensus; other implementation outcomes, such as costs of the intervention and satisfaction of the healthcare professionals, will also be evaluated. 									

Inclusion criteria:	All NHs already taking part in the pharmaceutical assistance programme of their canton, having a geriatric mission, and whose mean population age is over 65 will be able to participate.									

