Project assessments, procedures:	Participating NHs will be randomised in two groups. NHs allocated to the intervention group will hold a QC session on deprescribing, where a local consensus on the deprescribing of specific therapeutic classes will be elaborated.									
	The effects will be assessed using anonymous data on the drug consumption of the NH (already routinely collected for the administrative monitoring of the pharmaceutical assistance programme) and NH-level data on falls, hospitalisation, emergency events and death. The implementation outcomes will be evaluated with questionnaires to health care professionals of the intervention group at baseline, 3 months and 12 months.									
Number of Participants:	62 NHs will be included in this project, 31 in each group (intervention and control). Assuming a normal distribution of the reduction in PIMs proportion and a standard deviation of 7.5%, similar between the two groups, this number of participant will allow for the detection of a 20% relative reduction in the primary outcome, from 22.8% to 18.2%, with 80% power.									
Project Duration:	From December 2017 to March 2019 (possible extension to March 2020)									
Project Centre(s):	Single-centre; the intervention will take place in multiple NHs in the cantons of Vaud and Fribourg.									
Statistical Considerations:	The inclusion of 62 NH will allow for the detection of a 20% relative reduction in the use of PIMs with 80% power.									
	The main outcome will be assessed using a generalised linear regression model taking the difference at 12 months in overall PIM proportion as dependent variable. The secondary outcomes will be assessed using the same methodology. The 5% level of significance will be considered for all analyses.									
Other methodological Considerations:	No other methodological considerations.									
Risk-Benefit statement:	In previous studies of deprescribing in older people residing in nursing homes, very few adverse events occurred, none of them serious. Moreover, physicians will retain complete control over NH residents' treatments during the study. It is thus estimated that the intervention poses little to no risk compared to usual care. Possible benefits include a reduced mortality rate and fewer adverse drug reactions, as well as fewer hospital stays and reduced consumption of acute care. The risk-benefits balance of this project is estimated to be clearly positive.									

ABBREVIATIONS

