7.2 Assessments of primary outcome

The primary endpoint of this study will be the difference in the overall proportion of PIMs used in each NH between baseline and 12 months. This endpoint will be assessed using the drug consumption data collected by the CPC monitoring team for the monitoring of the two cantonal PAPs; these data will be anonymised before transmission to the investigators (see section 5.3, page 13 for data collection).

PIM status for each line of drug consumption data will be assessed using a custom screening tool combining criterion from the Beers' list [6], STOPP tool [31] and NORGEP-NH list [32]. This tool will classify each data line as "not inappropriate", "possibly inappropriate" or "probably inappropriate". At both time points, the proportion of PIM will be computed for each NH as the ratio of the number of galenic units classified as "inappropriate" (sum of possibly and surely inappropriate) to the total number of galenic units used in the NH over the course of the past year. The primary outcome will be the difference of the two resulting proportions.

The co-primary endpoint for this study will be the change in the number of potentially inappropriate DDD/res between baseline and 12 months. For each NH, the total number of DDD used will be computed according to the active ingredient of the drug and its administration route. The total number of DDD will be divided by the total number of days spent in the NH for the year to calculate the number of DDD/res.

Rationale for the addition of a co-primary outcome: work on the same topic carried out by the investigators during the study revealed that the change in number of potentially inappropriate DDD/res is a more robust outcome, as it captures the adaptations of the doses of PIMs used and, unlike the proportion of potentially inappropriate galenic, is independent of the total amount of drugs. This addition of a co-

primary outcome was decided before the completion of data collection, and before any analysis of the data collected to date had been carried out. The investigators stress that this addition is in no way related to a supposed lack of effectiveness of the intervention; rather, it has been decided to try and reflect the effects of the intervention in the most accurate way possible.

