8. STATISTICAL METHODOLOGY

8.1 Determination of sample size

Based on the retrospective data collected for the administrative monitoring of the Fribourg PAP, the mean proportion of PIM in the NH of Fribourg in 2015 was 22.8% (SD 6.3%). The natural year-on-year variation of the outcome was calculated between 2014 and 2015: the mean difference is 0.8% (IC₉₅ -1.1% - 2.7%, SD 5.3%); the correlation coefficient ρ between values of the outcome for 2014 and 2015 is 0.54 (IC₉₅ 0.29 – 0.72).

Studies of deprescribing have shown relative reductions in the number of PIMs ranging from 6.4% [33] to 31%[34]; one of the largest studies so far showed a 19.7% reduction in the number of PIMs [30]. Our hypothesis is that the intervention proposed in this study will reduce the proportion of PIMs used by 20%, in relative term.

We aim to detect an absolute difference of 4.6% ($22.8\% \times 0.2$) in the one-year reduction of the proportion of PIM between the control and intervention groups. The standard deviation of the difference at 12 months (SD_{diff}) was estimated with the following formula, assuming that the standard deviation at baseline and 12 months were the same and equal to 6.3%:

$$Var_{diff} = Var_{baseline} + Var_{12\;months} - 2 \cdot \rho \cdot SD_{baseline} \cdot SD_{12\;months}$$

By varying the correlation coefficient ρ along the confidence interval, plausible values of SD_{diff} were estimated to be between 4.1% (ρ =0.7) and 7.5% (ρ =0.3). A value of ρ =0.3 (SD_{diff} = 7.5%) was chosenas a conservative estimate for the calculation of the sample size, given the moderate correlation between the values for 2014 and 2015. To detect a difference between a mean difference of 0 in the control group and 4.6 in the intervention group (common SD of 7.5%, risks of α and β errors of 5% and 20%), 66NH, 33 per group, will have to be included. With an optimistic estimate of ρ = 0.7, the number of NH to include would decrease to 36. However, as this could lead to a lack of statistical power, a conservative estimate has been preferred.

Given that 82 NH meet inclusion criteria in the canton of Vaud and 42 in the canton of Fribourg, we expect that approximately 2/3 of the participants will be recruited in Vaud, and 1/3 in Fribourg.

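### The co-primary outcome, inappropriate DDD per resident-day, is absent from the SAP, and neither document says whether one or both primary outcomes must succeed

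*Protocol*

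**What the plan says.** **Protocol.** The synopsis (Endpoints) states "The co-primary outcome is the change at 12 months, relative to baseline, in the number of potentially inappropriate defined daily dose per average resident", per day. Section 4.2 repeats this. Section 7.2 says "The co-primary endpoint for this study will be the change in the number of potentially inappropriate DDD/res between baseline and 12 months", and explains that the outcome was added during the study because the investigators consider it more robust than the galenic-unit proportion. Section 8.2 gives its formula, with days spent in the home in the denominator, and says it is computed "Using the same dataset as for the primary outcome and the same appropriateness classification tool". For the secondary versions by category, section 8.2 says "the change between baseline and 12 months will be computed for each category as for the co-primary outcome". Section 8.3 then says "The same analysis will be carried out for the co-primary outcome", but names the dependent variable as a number of DDD, without the resident-day denominator.

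On error control, the synopsis says "The 5% level of significance will be considered for all analyses". Section 8.3 sets two-sided 0.05 for the primary analysis. No testing order, alpha split or either/both rule is given. Section 8.1 sizes the trial on the galenic-unit proportion alone.

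**SAP.** The Primary outcome section has the galenic-unit proportion only. The Secondary outcomes, Descriptive analysis and Inferential analysis sections cover the proportions of possibly and of probably inappropriate DDDs. The available SAP text mentions neither DDD/res nor a co-primary outcome.

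**The concern.** There are two linked defects.

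First, the documents disagree on what the trial's primary tests are. Under the protocol there are two, each with a model. Under the SAP there is one. The SAP's DDD proportions cannot stand in for DDD/res, because their denominator is total DDDs and not resident-days. Section 7.2 gives independence from total drug volume as a reason for choosing DDD/res, and a proportion lacks that property.

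Second, even under the protocol alone, a split result (one outcome significant, the other not) has no pre-specified reading. It could be reported as success, failure or a mixed result, and the choice would be made after the data are seen. This matters more because DDD/res was added mid-study. The protocol takes care to say that the addition preceded any analysis, and a SAP that omits the outcome weakens that assurance.

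**Working it through.** **1. Outcomes side by side**

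| Outcome | Protocol | SAP |
|---|---|---|
| Change in inappropriate galenic-unit proportion | Primary (4.2, 7.2, 8.2, 8.3) | Primary |
| Change in inappropriate DDD/res, overall | Co-primary (synopsis, 4.2, 7.2, 8.2, 8.3) | Absent |
| Change in DDD/res, possibly and probably inappropriate | Secondary (8.2) | Absent |
| Change in proportion of DDDs, possibly and probably inappropriate | Secondary (8.2) | Secondary |

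**2. Either outcome suffices.** Family-wise error = 1 − P(|Z1| < 1.96, |Z2| < 1.96), with Z1 and Z2 bivariate normal with correlation r. The documents give no r, so a range is shown.

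| r | 0 | 0.5 | 0.7 | 0.9 |
|---|---|---|---|---|
| Error | 0.0975 | 0.0907 | 0.0835 | 0.0704 |

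**3. Both must succeed.** Error is at most 5%; the cost is power.

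Inputs from Protocol 8.1: difference 4.6 points ("To detect a difference between a mean difference of 0 in the control group and 4.6 in the intervention group"), SD 6.3, planning correlation between years 0.3, observed correlation 0.54, 33 homes per group. The synopsis has 31 per group.

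The protocol's own figure comes first. It uses a change-score SD of 7.5: n per group = 2 × (7.5/4.6)² × (z_alpha + z_beta)². With one-sided 5% this is 2 × 2.658 × (1.645 + 0.842)² = 32.9, so 33 per group and 66 homes, as stated. With the two-sided 5% of section 8.3 it is 2 × 2.658 × (1.960 + 0.842)² = 41.7, so 42 per group and 84 homes. The 66 therefore reproduces only one-sided. That is a separate matter, but it affects which power baseline is used below.

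The planned model adjusts for baseline, so the residual SD is 6.3 × √(1 − 0.3²) = 6.01, or 6.3 × √(1 − 0.54²) = 5.30. Single-outcome power is from the noncentral t with 2n − 3 df (2n − 2 for the change score), two-sided 5%. For example, at n = 33 the noncentrality is 4.6/(6.01 × √(2/33)) = 3.11 and power is 0.865. Joint power is Φ₂(z_p, z_p; r), where p is the single-outcome power, assumed equal for DDD/res.

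| Basis | n per group | One outcome | Both: r = 0 | 0.5 | 0.7 | 0.9 |
|---|---|---|---|---|---|---|
| Adjusted, correlation 0.3 | 33 | 0.865 | 0.748 | 0.779 | 0.798 | 0.826 |
| Adjusted, correlation 0.3 | 31 | 0.842 | 0.710 | 0.747 | 0.768 | 0.799 |
| Adjusted, correlation 0.54 | 33 | 0.934 | 0.873 | 0.887 | 0.896 | 0.912 |
| Change score, SD 7.5 | 33 | 0.689 | 0.475 | 0.544 | 0.578 | 0.626 |

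Equal power for DDD/res is an assumption, because the documents give no effect size or SD for it. On the first basis, with r = 0.5, power for DDD/res of 0.50, 0.70 or 0.90 gives joint power of 0.475, 0.649 or 0.805. All figures ignore clustering of homes by physician, which would lower them.

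**The case against.** The SAP's date is not visible. It may predate the addition of DDD/res, which would make this a version lag and not a disagreement. That is plausible, but the SAP would still need updating, because it is the document an analyst will follow.

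The galenic-unit proportion is defined identically and adjusted for baseline in both documents, so its result need not differ. This stands: the SAP omits a second primary test and does not alter the first.

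The error inflation is conditional. Co-primary is often taken to mean that both outcomes must succeed, and then there is none. Section 8.3 also calls the galenic-unit proportion the main outcome, and section 8.1 sizes the trial on it, which hints at a hierarchy. But the protocol points other ways too: section 7.2 calls DDD/res the more robust outcome, while section 4.1 puts PIM consumption measured by DDD under the secondary objectives. No reading is stated, so 7.0% to 9.75% is the consequence of one possible reading, not the trial's established error rate.

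The power cost looks modest only on the baseline-adjusted basis. This is fair. On the protocol's change-score SD of 7.5, joint power at 33 per group is 48% to 63%. The adjusted basis is used as the main one because it is the planned analysis.

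**Conclusion.** The concern holds. The protocol defines a co-primary outcome with a formula and a model, and the SAP omits it together with its secondary versions. No rule links the two primary-level tests. The omission and the missing rule rest on the text alone and need no assumption.

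The size of the consequence depends on the rule eventually chosen. If either outcome suffices, family-wise error is 7.0% to 9.75% (assumed correlation 0.9 to 0). If both are required, power falls from about 86% to 75–83% at 33 per group and from about 84% to 71–80% at 31, assuming equal power for DDD/res, a year-to-year correlation of 0.3 and no clustering. With the observed correlation of 0.54, the fall at 33 per group is from about 93% to 87–91%.

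The missing denominator in section 8.3 is a wording slip, since sections 7.2 and 8.2 are clear. It still needs correcting: read literally, the outcome would scale with the size of the home. This must be fixed before analysis, because it decides what the trial's primary result is.

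**What to change.** 1. Add DDD/res to the SAP as co-primary, with the formula in Protocol 8.2 and the same baseline-adjusted model as the galenic-unit proportion. Add the secondary DDD/res outcomes of Protocol 8.2.
2. In Protocol 8.3, name the dependent variable as potentially inappropriate DDD/res. Align section 4.1 with the status given to DDD/res elsewhere.
3. Before any analysis by allocation group, state in both documents one success rule that holds 5% overall. The choice is the sponsor's:
   - **Fixed sequence**, for example the galenic-unit proportion at two-sided 5%, then DDD/res at two-sided 5% only if the first succeeds. This order follows the sample-size basis and costs the galenic test no power, but DDD/res can support a claim only after a galenic success. The sponsor should weigh that against the preference for DDD/res in section 7.2.
   - **Both required**, each at two-sided 5%. The cost is the joint power shown above.
   - **Holm.** On the adjusted basis with correlation 0.3, galenic power goes from about 86% to about 79% at 33 per group (84% to 76% at 31) if DDD/res shows no effect. If DDD/res has equal power, it goes only to about 83–85% (80–82% at 31).

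No new data are needed, since DDD/res comes from the dataset already collected for the primary outcome. The cost is amended wording in two documents, dated before group-level analysis.
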